### **GI symptoms using PRO / ObsRO questionnaire**

The GI symptom PRO consists of 6 items, 5 of which are scored using a 0 – 10 rating scale with item-appropriate end anchors to rate the symptom, The sixth item assesses bowel movement frequency during the past 24 hours, using 7 response options.

For GI symptom ObsRO, the following rules (as applicable in this study) are used for coding:

Over the last 2 weeks how often have you been troubled by abdominal pain or abdominal cramps?

0. Never
1. Rarely
2. Sometimes
3. Often
4. All the time

Over the last 2 weeks, how much of a problem have you had with bloating?

0. No problem
1. A minor problem
2. Some problem
3. A significant problem
4. A major problem

In the last 2 weeks, how much of a problem have you had with excessive wind?

0. No problem
1. A minor problem
2. Some problem
3. A significant problem
4. A major problem

Over the last 2 weeks, on average how often do your bowels move per day?

0. Less than once daily
1. 1-2 times per day
2. 3-4 times per day
3. 5-6 times a day
4. More than 6 times per day

In the last 2 weeks, how much of a problem have you had with loose stools?

0. No problem
1. A minor problem
2. Some problem
3. A significant problem
4. A major problem

How often during the last 2 weeks have you had an urgent need for your bowels to open or a sudden need for a toilet?

0. Never
1. Rarely
2. Sometimes
3. Often
4. All the time

How often during the last 2 weeks have you been woken from your sleep to open your bowels?

0. Never
1. Rarely
2. Sometimes
3. Often
4. All the time

Over the last 2 weeks, how often do your bowel motions float and require more than one flush?

0. Never
1. Rarely
2. Sometimes
3. Often
4. All the time

Over the last 2 weeks, how often have your bowel motions been oily or greasy?

0. Never
1. Rarely
2. Sometimes
3. Often
4. All the time

Over the last 2 weeks, how much of a problem have you had with foul smelling stools?

0. No problem
1. A minor problem
2. Some problem
3. A significant problem
4. A major problem

Over the last 2 weeks, how much of a problem have you had maintaining or getting to the weight you would like to be?

0. No problem
1. A minor problem
2. Some problem
3. A significant problem
4. A major problem

How often has the feeling of fatigue or of being tired and worn out been a problem for you during the last 2 weeks?

0. Never
1. Rarely
2. Sometimes
3. Often
4. All the time

The GI symptoms will be summarized and listed.

Suitable graphs (domain scores plot and waterfall plot) will be presented related to PROs. For this purpose, 95% CI may be reported if appropriate.

## **2.12 Biomarkers**

Not applicable.

## **2.13 Other Exploratory analyses**

Not applicable.

## **2.14 Interim analysis**

One interim analysis is planned in this study.

The interim analysis will be performed at end of Core phase (Week 48) that is after all patients complete Week 48, to assess the patient preference after 6 months with deferasirox FCT treatment in comparison to deferasirox DT. The primary analysis to evaluate the patient preference of FCT over DT will be performed at this interim. Along with primary analysis, all baseline, key efficacy and safety analyses will also be performed till Core phase.

### 3 Sample size calculation

Based on data from the ECLIPSE study (Taher et al 2018), the following assumptions have been made at Week 48, the patient preference for deferasirox FCT (formulation) is 45% and preference for deferasirox DT (formulation) is 25% and no preference to either of the formulations is 30%. This means the discordant pairs is 70 % (i.e. 70% preferred one formulation over another, 45 %) and concordant pairs= 30% (assuming same preference for each formulation, 15%).

At least 130 patients are needed at Week 48 to have 80% power to detect the difference of patient preference of 20% (i.e. 45% preference of FCT over DT and 25% preference of DT over FCT) at a two sided significance level of 0.05 using McNemar's test for matched pairs.

To allow for roughly 10% of subjects with missing measurement, a total of approximately 145 evaluable patients aged  $\geq 2$  years male or female with TDT or NTDT requiring chelation therapy due to iron overload, need to be enrolled. Patients may have been previously treated with iron chelators (other than deferasirox DT) or be chelation-naïve.

EAST 6.0 is used to calculate the sample size.

### 4 Change to protocol specified analyses

Not applicable.

### 5 Appendix

#### 5.1 Imputation rules

##### 5.1.1 Study drug

Not applicable.

##### 5.1.2 AE date imputation

AE date imputation is based only on a comparison of the partial AE start date to the treatment start date as mentioned in the [Table 5.1-2](#) below.

1. If the AE start date year value is missing, the date uncertainty is too high to impute a rational date. Therefore, if the AE year value is missing, the imputed AE start date is set to NULL.
2. If the AE start date year value is less than the treatment start date year value, the AE started before treatment. Therefore:
  - a. If the AE year is less than the treatment year and the AE month is missing, the imputed AE start date is set to the mid-year point (01JulYYYY).
  - b. Else if the AE year is less than the treatment year and the AE month is not missing, the imputed AE start date is set to the mid-month point (15MONYYYY).
3. If the AE start date year value is greater than the treatment start date year value, the AE started after treatment. Therefore:

- a. If the AE year is greater than the treatment year and the AE month is missing, the imputed AE start date is set to the year start point (01JanYYYY).
  - b. Else if the AE year is greater than the treatment year and the AE month is not missing, the imputed AE start date is set to the month start point (01MONYYYY).
4. If the AE start date year value is equal to the treatment start date year value:
- a. And the AE month is missing or the AE month is equal to the treatment start month, the imputed AE start date is set to one day after treatment start.
  - b. Else if the AE month is less than the treatment start month, the imputed AE start date is set to the mid-month point (15MONYYYY).
  - c. Else if the AE month is greater than the treatment start month, the imputed AE start date is set to the start month point (01MONYYYY).

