10.5.3.2 Adverse events (AEs)

Summary tables for adverse events (AEs) will include only AEs that started or worsened during the on-treatment period, the *treatment-emergent* AEs. The AEs will be summarized separately and compared for two treatment groups FCT (Week 25 to 48) and DT (Baseline Day 1 to Week 24).

The incidence of treatment-emergent adverse events (new or worsening from baseline) will be summarized by system organ class and or preferred term, severity (based on mild, moderate, severe, life threatening, death), type of adverse event, relation to study treatment. If a patient reported more than one AE with the same preferred term, the AE with the greatest severity will be presented. If a patient reported more than one AE within the same primary system organ class, the patient will be counted only once with the greatest severity at the system organ class level, where applicable.

Serious adverse events, non-serious adverse events and adverse events of special interest (AESI) which are specific gastrointestinal events during the on-treatment period will be tabulated.

Separate summaries will be provided for death, SAE, other significant AEs leading to discontinuation and AEs leading to dose adjustment (including study treatment discontinuation).

As appropriate, the incidence of AEs will be presented per 100 patient years of exposure.

All AEs, deaths and serious adverse events (including those from the pre and post-treatment periods) will be listed and those collected during the pre-treatment and post-treatment period will be flagged.

A graphical display of relative frequencies within system organ classes and relative risks, as appropriate, may be presented is required.

For AEs of special interest, time-to-event analysis will be performed, as appropriate and as described in the statistical analysis plan. Results will be tabulated and the Kaplan-Meier estimates for the cumulative rate will be plotted.

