| To evaluate the overall safety of deferasirox FCT compared with deferasirox DT  | Overall safety, as measured by frequency and severity of adverse events and changes in laboratory values of interest during deferasirox FCT (Week 25 to 48) compared with deferasirox DT (Baseline day 1 to Week 24) |
| To evaluate efficacy of deferasirox ( both DT and FCT) in decreasing serum ferritin levels  | Absolute and relative change from baseline ( Day 1) in serum ferritin on monthly basis   |

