### **2.1.1 General definitions**

#### **Study treatment**

In this and subsequent analysis plan module (TFL and PDS), the terms “investigational drug”, “study drug” and “study treatment” refers to deferasirox FCT as well as deferasirox DT.

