#### **Study treatment start and end date**

Study treatment start date is defined as the first date when a non-zero dose of study drug is administered and recorded on the Drug Administration Record (DAR) CRF page. Similarly, study drug end date is defined as the last date when a non-zero dose of study drug is administered and recorded on the DAR CRF page of the study.

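### Partial adverse-event dates are imputed only against the first study-drug dose, so in the planned DT-then-FCT sequence some FCT events can be counted under DT

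*SAP*

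**What the plan says.** SAP 5.1.2 opens by saying that "AE date imputation is based only on a comparison of the partial AE start date to the treatment start date". SAP 2.1.1 supplies the anchor: "Study treatment start date is defined as the first date when a non-zero dose of study drug is administered", and the term study drug "refers to deferasirox FCT as well as deferasirox DT". In the planned sequence the anchor is therefore the first DT dose. Neither the imputation text nor Table 5.1-2 mentions the FCT start.

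For partial dates that may fall on treatment the rules are:

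- Start year, with the month missing or equal to the start month: "the imputed AE start date is set to one day after treatment start".
- Start year, with a later month known: the first of that month.
- A later year: the first of the month if the month is known, otherwise 1 January.
- Year missing: no date is imputed.

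The safety comparison is by formulation period. Protocol 10.5.3.2 says "The AEs will be summarized separately and compared for two treatment groups FCT (Week 25 to 48) and DT", with DT covering Day 1 to Week 24. SAP Table 1.2.1 uses the same windows for the safety endpoint, and SAP 2.8.1 defines a risk difference by system organ class as FCT minus DT. The SAP does not say how an event with an imputed or missing date is assigned to DT or FCT, and it plans no sensitivity analysis for this.

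**The concern.** The rules can sort events into before and after the start of treatment. The formulation comparison needs a second division, before or after the FCT start, and nothing in the rules addresses it. Because possible on-treatment dates go to the earliest compatible day, an ambiguous event is pulled backwards in time. In a fixed DT-then-FCT order, backwards means towards DT.

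What is at stake is the adverse-event contrast between formulations. It is a secondary objective of an open-label, single-arm study in which each patient serves as the comparator, so the period assigned to an event is the treatment assigned to it. The planned time-to-event analysis of gastrointestinal events of special interest (SAP 2.8.1.1) would also be touched: an event in the start year with unknown month becomes an event one day after the first dose.

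**Working it through.** The plan gives no figure to reproduce, so the check applies its rules directly.

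**Inputs.** From the documents: the rules of SAP 5.1.2 and Table 5.1-2; DT on days 1-168; FCT on days 169-336 (first FCT dose on Week 25 day 1, Protocol Table 7-1 footnote 5); extension on FCT from day 337 for 48 weeks (SAP 2.1.1). Assumed: first doses spread evenly over the 365 days of a year, a constant event rate, all patients continuing, and the imputed date deciding the period.

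**One patient.** First dose 1 March, so FCT starts 168 days later, on 16 August. A true onset on 20 August is an FCT event. With the day missing it is imputed to 1 August, in DT. With the month missing it is imputed to 2 March, also in DT.

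**Day missing, all start dates.** An FCT event moves to DT only if it falls in the calendar month of the FCT start and FCT did not start on the 1st. For a month of L days, the mean number of affected days is (L - 1)/2. The day-weighted mean of L is (7 × 31² + 4 × 30² + 28²)/365 = 30.44, which gives (30.44 - 1)/2 = 14.7 days.

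- FCT to DT: 14.7/168 = 8.8%. DT to FCT: 0%.
- Event-days, core only: DT 168 + 14.7 = 182.7; FCT 168 - 14.7 = 153.3; ratio 153.3/182.7 = 0.84.

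**Month missing.** Applying the rules to every onset day and start date moves on average 129.1 of the 168 FCT days to DT, or 76.8%, and again 0% from DT to FCT. By start month the number moved runs from 32 days (June) to all 168 (January, and August to December). The core ratio is 38.9/297.1 = 0.13.

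**Extension events.** The same rules pull these back into Weeks 25-48: 4.4% of day-missing events (14.7/336) and 38.1% of month-missing events. A further 15.7% of month-missing extension events land in DT.

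- Day missing: FCT returns to 153.3 + 14.7 = 168.0; ratio 168.0/182.7 = 0.92.
- Month missing: ratio 166.9/350.0 = 0.48 on average, but FCT exceeds DT for start months February to June. For June, DT has 168 + 32 = 200 days and FCT has 136 + 228 = 364.

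**Period 2 switchers from FCT to DT.** With switches spaced weekly from 197 to 302 days after the first dose and events counted by actual treatment, 17% of day-missing events in the later DT stretch move to FCT.

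**All core events together.** Let s be the share of events lacking only the day. With equal true rates, the FCT/DT event ratio is (1 - 0.088s)/(1 + 0.088s).

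| Assumed s | Ratio |
|---|---|
| 5% | 0.991 |
| 10% | 0.983 |
| 20% | 0.965 |

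If 10% lack the day and a further 2% lack the month, the share moved is 0.10 × 0.088 + 0.02 × 0.768 = 0.024, and the ratio is 0.976/1.024 = 0.95.

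**The case against.** The strongest reply is that Table 5.1-2 labels its outcomes only as before or after treatment start. It can be read as a rule for treatment emergence, and the SAP never says that the imputed date also settles the formulation. This stands as a condition on the finding. It does not remove the gap, because no other rule is given for events whose partial date spans the changeover.

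Second, missing months may be rare. Protocol 8.1.1 has events sought at each visit with start and end dates determined, visits are at most four weeks apart, and Protocol 9.4 provides queries for missing values. Nothing in the documents suggests that unknown months are common, so the 77% describes one kind of missing date and not the likely effect on the trial.

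Third, a reader might infer that the error has a fixed direction and always favours FCT. The documents do not support that. Protocol 4.2 allows a switch from FCT to DT in Period 2, which opens the opposite path if events are counted by actual treatment. Extension events drawn back into Weeks 25-48 offset part of the shift, and for month-missing dates they can reverse it in some start months.

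Fourth, SAP 2.8.1 counts each patient once per category. Moving an event changes a reported percentage only if the patient had no other such event in the period that gains it, or none left in the period that loses it. The percentages of events moved are therefore not shifts in reported risk. SAP 2.7.2 also plans no formal testing of secondary endpoints, and the risk-difference plot is optional.

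**Conclusion.** The point holds in a conditional form. The imputation has no FCT anchor. If imputed dates decide the period, the planned sequence lets partially dated events move from FCT to DT but not from DT to FCT: about 9% of day-missing and 77% of month-missing Week 25-48 events. On average this favours FCT. Among day-missing events the FCT/DT ratio is 0.84 for core events alone and 0.92 with extension events included.

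The overall effect is probably small, about 0.98 if 10% of events lack only the day, and would matter more if months were often missing. These figures rest on uniform start dates, a constant event rate and an assumed share of partial dates, which the documents do not state. They do not show that the safety comparison will be materially biased. They show that a stated rule can misplace events across the changeover and that the plan has no check on it. This is a minor point with an inexpensive remedy.

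**What to change.** Add to SAP 5.1.2:

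1. Compare each partial date with the patient's actual DT/FCT switch dates and the extension start, as well as with the first dose.
2. When the date is compatible with more than one formulation period or phase, assign the event using the visit at which it was first reported, where the data hold that visit. The Week 24 visit is scheduled at the changeover, give or take 7 days, so this should settle many cases. Protocol 8.1.1 does not list the reporting visit among the items determined for each event, so its availability needs checking first.
3. Flag events that remain unresolved, and present the DT-versus-FCT summary twice: once with all of them in the earlier period and once with all in the later.

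Both versions are needed, because moving the anchor to the FCT start only reverses the error: the day-missing core ratio becomes 182.7/153.3 = 1.19. If 10% of events lacked only the day and none could be settled by visit, the two summaries would bracket the core event ratio between about 0.983 and 1.018.

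The cost is a short derivation rule, one flag and one repeated table. No new data collection is proposed.

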4.1 Description of study design

This is an open-label, multicenter, single arm, phase II study aimed at collecting data on preference for iron chelation therapy in patients with transfusion-dependent thalassemia (TDT) or non-transfusion-dependent thalassemia (NTDT) throughout a 48 week treatment period.

It is a pre-requisite for the patient to provide written consent for participation in this study. This must be in place prior to performing any study-related procedures or assessments, including those described at the screening visit (please refer to [Table 7-1](#) and [Table 7-2](#)

Patients will undergo up to 4 weeks of screening and if deemed eligible, will receive deferasirox dispersible tablet (DT) formulation for 24 weeks. At the completion of 24 weeks patients will be transitioned on Week 25 to an equivalent dose of the deferasirox film coated tablet (FCT) formulation and continue treatment until Week 48 (EOT of Core Phase).

Patients can then continue deferasirox FCT formulation as per the judgment of the investigator, through an extension phase for a maximum of 12 months from the last dose of deferasirox FCT received at the end of period 2 in the Core Phase.

If one of the end of study criterion is met at any time during the study, the patient must discontinue from the study and should complete the Study Evaluation Completion (SEC - visit number 777). Please refer to [Section 4.4](#) .

Patients must be followed up for 30 days after the last dose of study drug for safety evaluation (safety follow up visit).

- Core Phase:
 - Screening phase which lasts for a maximum of 4 weeks to determine patient eligibility followed by
 - Baseline visit (day 1)
 - Period 1: deferasirox DT as 20-40 mg/kg/day dose regimen of dispersible tablet formulation for 24 weeks followed by
 - Period 2: deferasirox FCT as 14-28 mg/kg/day dose regimen of film- coated tablet for 24 weeks.
- Extension Phase:

Deferasirox FCT as 14-28 mg/kg/day dose regimen of film-coated tablet.
- PRO Validation Sub-study:
 - Patients in Egypt and Thailand may participate in this optional sub-study [sub-study protocol will only be submitted in the participating countries]

[figure not shown]
Participation in the extension phase is optional. Please refer to [Section 4.4](#) for EOS criteria.

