8.1 Adverse events

8.1.1 Definitions and reporting

An adverse event is defined as the appearance of (or worsening of any pre-existing) undesirable sign(s), symptom(s), or medical condition(s) that occur after patient's signed informed consent has been obtained.

Abnormal laboratory values or test results occurring after informed consent constitute adverse events only if they induce clinical signs or symptoms, are considered clinically significant, require therapy (e.g., hematologic abnormality that requires transfusion or hematological stem cell support), or require changes in study medication(s).

Except for screening failures, adverse events that begin or worsen after informed consent should be recorded in the Adverse Events eCRF. Conditions that were already present at the time of informed consent should be recorded in the Relevant Medical History/Current Medical Conditions eCRF page. Adverse event monitoring should be continued for at least 30 days (or 5 half-lives, whichever is longer) following the last dose of study treatment. Adverse events (including lab abnormalities that constitute AEs) should be described using a diagnosis whenever possible, rather than individual underlying signs and symptoms. When a clear diagnosis cannot be identified, each sign or symptom should be reported as a separate Adverse Event.

Severity of adverse events will be assessed as mild, moderate, or severe. Information about deaths will be collected through an SEC form.

The occurrence of adverse events should be sought by non-directive questioning of the patient during the screening process after signing informed consent and at each visit during the study. Adverse events also may be detected when they are volunteered by the patient during the screening process or between visits, or through physical examination, laboratory test, or other assessments. As far as possible, each adverse event should be evaluated to determine:

1. The severity grade (mild, moderate, or severe)
2. Its duration (Start and end dates or Ongoing at End of Study)
3. Its relationship to the study treatment (Reasonable possibility that AE is related: suspected vs non-suspected)
4. Action taken with respect to study or investigational treatment (none, dose adjusted, temporarily interrupted, permanently discontinued, unknown, not applicable)
5. Whether medication or therapy was given (no concomitant medication/non-drug therapy, concomitant medication/non-drug therapy)

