## 2.8 Safety analyses

For all safety analyses, the Safety Set (SAF) will be used. All listings and summaries will be presented by treatment group (wherever applicable) and by TDT and NTDT. In addition, all key safety summaries will be reported separately for all age groups (defined earlier in [Section 2.2.1](#)). The safety analysis will also be presented separately for core and extension phases of the study.

The overall observation period will be divided into three mutually exclusive segments:

1. Pre-treatment period: from day of patient's informed consent to the day before first dose of study medication.
2. On-treatment period: from day of first dose of study medication to 30 days after last dose of study medication.
3. Post-treatment period: starting at day 30+1 after last dose of study medication.

All serious adverse events (SAEs), non-serious adverse events (AEs) and adverse events of special interest (AESI) which are specific gastrointestinal events during the on-treatment period will be summarized.

All data, regardless of observation period, will be listed. Safety assessments starting during the pre-treatment or post-treatment period will be flagged in the listings. Safety assessments starting prior to study day 1 will appear with negative study day in the listings.

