### 2.8.1 Adverse events (AEs)

Summary tables for AEs will include only AEs that started or worsened during the on-treatment period, the *treatment-emergent* AEs.

The incidence of treatment-emergent AEs (new or worsening from baseline) will be summarized by system organ class and or preferred term, severity (mild, moderate, severe), type of adverse event, relation to study treatment. If a patient reported more than one AE with the same preferred term, the AE with the greatest severity will be presented. If a patient reported more than one AE within the same primary system organ class, the patient will be counted only once with the greatest severity at the system organ class level, where applicable.

Severity is captured in CRF as per CTCAE V 4.03 grades. The mapping from CTCAE to severity grade is given below:

- Grade 1=Mild
- Grade 2= Moderate

- Grade 3= Severe
- Grade 4 = Life- threatening
- Grade 5= Death related to AE

In this study the grade  $\geq 3$  will be considered as severe.

As appropriate, the incidence of AEs will be presented per 100 patient years of exposure.

The following adverse event summaries will be produced by treatment for Safety Set:

- Adverse events (overall and severe), regardless of study drug relationship by primary system organ class and preferred term
- Adverse events, regardless of study drug relationship by primary system organ class and preferred term and severity
- Adverse events (overall and severe), with suspected study drug relationship by primary system organ class and by preferred term
- Serious adverse events (overall and severe), regardless of study drug relationship, by primary system organ class and preferred term
- Adverse events leading to study drug discontinuation (overall and severe), regardless of study drug relationship, by primary system organ class and preferred term
- Adverse events requiring dose adjustment or study-drug interruption (overall and severe), regardless of study drug relationship, by primary system organ class and preferred term
- Adverse events requiring additional therapy (overall and severe), regardless of study drug relationship, by primary system organ class and preferred term

The incidences listed above will additionally be summarized by preferred term.

- Deaths by primary system organ class and preferred term.
- Non-serious adverse events, regardless of study drug relationship, by primary system organ class and preferred term (for clinicaltrials.gov purpose)

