**Table 5.1-2: AE date imputation**

|                        | MON  | MON < CFM              | MON = CFM              | MON > CFM              |
|------------------------|--|------------------------|------------------------|------------------------|
|                        | MISSING  |                        |                        |                        |
| YYYY MISSING           | NULL   | NULL                   | NULL                   | NULL                   |
|                        | Uncertain  | Uncertain              | Uncertain              | Uncertain              |
| YYYY < CFY             | ( D ) = 01JULYYYY  | ( C ) = 15MONYYYY      | ( C ) = 15MONYYYY      | ( C ) = 15MONYYYY      |
|                        | Before Treatment Start   | Before Treatment Start | Before Treatment Start | Before Treatment Start |
| YYYY = CFY             | (B)= TRTSTD+1  | ( C ) = 15MONYYYY      | (A)= TRTSTD+1          | (A)= 01MONYYYY         |
|                        | Uncertain  | Before Treatment Start | Uncertain              | After Treatment Start  |
| YYYY > CFY             | (E)= 01JANYYYY   | (A)= 01MONYYYY         | (A)= 01MONYYYY         | (A)= 01MONYYYY         |
|                        | After Treatment Start  | After Treatment Start  | After Treatment Start  | After Treatment Start  |
| Before Treatment Start | Partial indicates date prior to Treatment Start Date                   |                        |                        |                        |
| After Treatment Start  | Partial indicates date after Treatment Start Date                      |                        |                        |                        |
| Uncertain              | Partial insufficient to determine relationship to Treatment Start Date |                        |                        |                        |
| LEGEND:         |  |                        |                        |                        |
| (A)                    | MAX(01MONYYYY,TRTSTD+1)  |                        |                        |                        |
| (B)                    | TRTSTD+1   |                        |                        |                        |
| (C)                    | 15MONYYYY  |                        |                        |                        |
| (D)                    | 01JULYYYY  |                        |                        |                        |

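### The AE start-date rule ignores the recorded end date, so some partially dated screening events that ended before the first dose are counted as treatment-emergent under DT

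*SAP*

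**What the plan says.** SAP 5.1.2 opens by limiting what the rule may use: "AE date imputation is based only on a comparison of the partial AE start date to the treatment start date". Under rule 4a, when the AE year equals the treatment start year and the AE month is missing or equals the treatment start month, "the imputed AE start date is set to one day after treatment start". Table 5.1-2 gives the same result (TRTSTD+1) and labels those cells uncertain, which its legend explains as "Partial insufficient to determine relationship to Treatment Start Date". No later part of SAP 5.1 corrects the result: section 5.1.3.3, on other imputations, is marked not applicable.

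Four further provisions matter:

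- Recording starts before dosing. Protocol 8.1.1 says that, screening failures aside, "adverse events that begin or worsen after informed consent should be recorded in the Adverse Events eCRF". Protocol 4.1 says: "Patients will undergo up to 4 weeks of screening and if deemed eligible, will receive deferasirox dispersible tablet (DT) formulation for 24 weeks".
- The end date is among the items to be determined for each event. Protocol 8.1.1 lists "Its duration (Start and end dates or Ongoing at End of Study".
- SAP 2.8 defines the relevant segment as "On-treatment period: from day of first dose of study medication to 30 days after last dose of study medication".
- SAP 2.8.1 says "Summary tables for AEs will include only AEs that started or worsened during the on-treatment period".

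**The concern.** An event that was over before the first dose can neither have started nor worsened on treatment, so under SAP 2.8 and 2.8.1 it does not belong in the treatment-emergent tables. Rule 4a puts it there whenever the start date is partial and falls in the cells described above, even if a complete end date shows when it finished. The record then has a start later than its end.

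The error has one direction. Every patient is planned to begin on DT, so a misplaced event normally lands on study day 2 of the DT period. SAP 2.8.1 plans a risk difference of FCT minus DT by system organ class, and a spurious DT event makes FCT look slightly better. The same event could enter the incidence per 100 patient-years. If it belongs to a gastrointestinal group of special interest, it could also appear as a day-2 event in the Kaplan-Meier analysis of SAP 2.8.1.1.

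**Working it through.** The documents give no figure for this point, so there is none to reproduce. The check applies the rule as written to sample records and then asks how often it would misplace an event.

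**Step 1. The rule applied to records.** The first dose is taken as 20 June 2018.

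| Recorded start | Recorded end | Imputed start | After its own end? | Treatment-emergent? |
|---|---|---|---|---|
| June 2018, day missing | 12 June | 21 June | yes, by 9 days | yes (wrong) |
| 2018, day and month missing | 12 June | 21 June | yes | yes (wrong) |
| 2018, day and month missing | 28 May | 21 June | yes | yes (wrong) |
| May 2018, day missing | 28 May | 15 May | no | no (right) |
| May 2018, day missing | 10 May | 15 May | yes | no (right) |
| year missing | 12 June | none | – | no |

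The first three rows show the defect. The fifth shows that rule 4b can also give a start after the end, but without changing the classification.

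**Step 2. Share moved when only the start day is missing.** The 4-week maximum for screening is Protocol 4.1's. The other inputs are assumptions: screening lasts the full 28 days, first-dose day d is uniform over a 30-day month, and the start falls uniformly b = 1 to 28 days before the first dose. An event lasting L days has ended before the first dose if b ≥ L. It falls in the first-dose month if b ≤ d − 1. Out of 30 × 28 = 840 combinations, the number meeting both conditions is

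N(L) = sum over d = 1 to 30 of max(0, min(d − 1, 28) − (L − 1)).

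- L = 1: (1 + … + 28) + 28 = 406 + 28 = 434; 434/840 = 52%.
- L = 7: (1 + … + 22) + 22 = 253 + 22 = 275; 275/840 = 33%.
- L = 14: (1 + … + 15) + 15 = 120 + 15 = 135; 135/840 = 16%.

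If the denominator is restricted to events already ended, 30 × (29 − L), the shares are 434/840 = 52%, 275/660 = 42% and 135/450 = 30%.

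A check of one-day events over a real calendar year (365 first-dose days × 28 start days = 10,220) gives 5,348 moved, again 52%.

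**Step 3. Month also missing.** The same one-day enumeration gives 9,814/10,220 = 96%. The remaining 406 (28 + 27 + … + 1) started in the previous calendar year, where rule 2a keeps them before treatment. Where the recorded year is the treatment year, all are moved.

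**Step 4. Effect on the risk difference.** In SAP Table 2-1 the DT risk is DTE/(DTE + DTN). If the denominator were the planned 145 patients, one spurious patient in a system organ class would lower FCT minus DT by 1/145 = 0.7 percentage points. A patient already counted in that class under DT would add nothing.

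**The case against.** The strongest defence is that moving an uncertain onset to on-treatment is a common and cautious convention, and Table 5.1-2 labels the cells openly. That stands for events still ongoing at the first dose, for those that ended on or after it, and for those with no usable end date. It does not cover an event with an end date before the first dose, because the relationship to treatment start is then known and the table's reason for the default no longer applies.

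The defence is also right about scale. Fully dated events are untouched, as are those with a known earlier month or an earlier year. Protocol 8.1.1 asks for dates as far as possible, so a record without a start day may lack a full end date too. Protocol 9.4 provides for queries on discrepancies and missing values, which should leave few such records. Flagging pre-treatment events in listings does not change the start date used for the tables.

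Three stronger inferences are tempting, and the documents do not support them:

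- A reader might infer that half of all screening events become treatment-emergent. The 52% applies only to one-day events with the start day missing, and it falls quickly as events last longer.
- A reader might expect negative durations in the report. SAP 2.8.1 plans no table of AE duration.
- A reader might infer that all AE tables are inflated. Causality is the investigator's assessment, and an event resolved before dosing should not be marked as suspected or as leading to dose change or discontinuation. Those tables should be largely unaffected.

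**Conclusion.** The rule is wrong as written for one narrow class: partially dated screening events in the treatment-start year, with the month missing or equal to the first-dose month, and with an end date that places them wholly before the first dose. For these it contradicts the SAP's own definition of treatment-emergent. The consequence is a small, one-directional inflation of all-causality DT counts.

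The number of affected events cannot be derived from the documents and is probably small. The shares of 52%, 33% and 16% rest on a full 28-day screening period, a 30-day month, uniform timing and the stated event lengths. They apply only to screening events lacking the start day. The primary preference endpoint does not use AE dates and is unaffected. This is a minor correction worth making, not evidence that the safety comparison is materially biased.

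**What to change.** In SAP 5.1.2 and Table 5.1-2, the sponsor should add two conditions that take precedence over the existing rules:

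1. If the AE end date, or the latest date compatible with a partial end date, is before the first dose, the event is classed as pre-treatment.
2. No imputed start date may be later than the AE end date; where it would be, the start is set to the end date.

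The opening sentence of 5.1.2 must change to match, since it now confines the comparison to the two start dates. The TRTSTD+1 default should remain for events that are ongoing, ended on or after the first dose, or have an uninformative end date. In the first record of Step 1 the start moves from 21 June to 12 June and the event leaves the treatment-emergent tables. No true on-treatment event is lost: one that ended on the first-dose day would be capped to that day, which is already inside the on-treatment period.

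The cost is a short SAP amendment, a revised table and two programming conditions on data already collected. The SAP's document history records an interim database lock before April 2021, and SAP 2.14 schedules key safety analyses at that point. Any core-phase AE tables already produced would need a rerun if affected records exist.
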